### 1.3.1 Clinical Pharmacokinetics and Product Metabolism

JZP-110 is eliminated primarily via the renal route, with at least 90% of the dose being excreted as unchanged drug within 48 hours. Following single dosing and repeated doses administered twice daily, JZP-110 exposure was dose-proportional, absorption (time to maximum plasma concentration [ $t_{max}$ ]: 1.3 to 3.0 hours) and elimination ( $t_{1/2}$ : 5 to 7.6 hours) were relatively rapid, and steady state was reached in 3 days. JZP-110 displayed linear PK during 14 days of dosing over the dose range of 200 to 1000 mg per day. Limited accumulation and no enzyme auto-induction were evident.

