### 6.13.2 Pharmacokinetic Parameters

Plasma PK parameters to be calculated for JZP-110 concentrations will include, but may not be limited to, the following, as appropriate:

AUC 0-t	Area under the plasma concentration versus time curve from time 0 to t hours, the last detectable concentration, calculated by means of the trapezoidal rule
AUC 0-inf	Area under the plasma concentration versus time curve from time 0 to infinity, calculated as $AUC = AUC_{0-t} + C_t / K_{el}$ , where $C_t$ is concentration at time t, and $K_{el}$ is the elimination rate constant estimated from the fitted terminal elimination phase (see $K_{el}$ )
$C_{max}$	Maximum plasma drug concentration
$T_{max}$	Time to reach $C_{max}$
$t_{1/2}$	Apparent terminal elimination half-life, calculated as $\ln(2) / K_{el}$
$K_{el}$	Apparent elimination rate constant estimated by unweighted log-linear regression of the last portion of the plasma concentration profile. This log-linear regression will be fitted according to the least-squares approach. Starting with the last 3 quantifiable measurements and stepping back, the best fit will be determined by minimizing the residual sums of squares; the time interval and the number of time points used for this optimal fit will be provided.
CL/F	Apparent oral clearance (calculated as Dose/AUC inf )
Vd/F	Apparent oral volume of distribution (calculated as oral clearance/ $K_{el}$ )

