## 3. STUDY DESIGN

### 3.1. GENERAL DESCRIPTION

This is a 4-week, multicenter, randomized, double-blind, placebo controlled, ascending dose, 4-period crossover study designed to evaluate the safety, tolerability, efficacy, and PK of JZP-110 (75, 150, and 300 mg) in the treatment of excessive sleepiness in adult subjects with idiopathic PD. Depending on study center capabilities, subjects will have the option of enrolling into 1 of 2 groups: Group 1 and Group 2. Subjects enrolled in Group 1 will undergo both objective (MWT) and subjective (ESS) assessments of sleepiness. Subjects enrolled in Group 2 will undergo only the subjective (ESS) assessment of sleepiness. Following completion of the Screening and Baseline visits, approximately 49 eligible subjects will be randomly assigned (3:3:1) to 1 of 3 treatment sequences in order to have approximately

34 subjects complete Treatment Sequences A and B, and 6 subjects complete Treatment Sequence C (Table 1). There will be no stratification based on group.

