## 18.3. PHARMACOKINETIC PARAMETERS

For PK parameter calculations, pre-dose samples that are BLQ or missing will be assigned a numerical value of zero. Any other BLQ concentrations will be assigned a value of zero if they precede quantifiable samples in the initial portion of the profile. A BLQ value that occurs between quantifiable data points, especially prior to  $C_{max}$ , will be evaluated to determine if an assigned concentration of zero makes sense, or if exclusion of the data (flagged out and treated as missing) is warranted. Following  $C_{max}$ , BLQ values embedded between 2 quantifiable data points will be treated as missing when calculating PK parameters. If a BLQ value occurs at the end of the collection interval (after the last quantifiable concentration), it will be set to zero. If consecutive BLQ concentrations are followed by quantifiable concentrations in the terminal portion of the concentration curve, these quantified values will be excluded from the PK analysis by setting them to missing, unless otherwise warranted by the concentration-time profile. Actual elapsed time from dosing on active treatment visits will be used for PK parameter calculations.

Plasma PK parameters to be calculated for JZP-110 concentrations by non-compartmental methods will include, but may not be limited to the following, as appropriate:

AUC 0-t,ss	Area under the plasma concentration-time curve from time zero (pre-dose) to time of last quantifiable concentration at time t, calculated by the Linear trapezoidal / Linear Interpolation summation method.
-----------------------	--

$C_{max,ss}$	Maximum plasma concentration, obtained directly from the observed concentration versus time data.
$t_{max,ss}$	Time of maximum plasma concentration, obtained directly from the observed concentration versus time data.
$t_{1/2}$	Apparent terminal elimination half-life, determined as $\ln(2)/K_{el}$ .
$K_{el}$	Apparent terminal elimination rate constant estimated by unweighted log-linear regression of the last portion of the plasma concentration profile.
$AUC_{0-tau}$	Area under the plasma concentration-time curve from time zero (pre-dose) through the dosing interval. Given the 24 hour dosing interval and blood collections for PK available through 8 hours, the estimated value will reflect an extrapolation and should be considered with caution.
$CL/F_{ss}$	Apparent oral systemic clearance, calculated as $Dose/AUC_{0-tau}$ .

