$Vd/F_{ss}$	Apparent oral volume of distribution, calculated as $Dose/K_{el} \times AUC_{0-tau}$ .

In addition, dose normalized  $AUC_{0-t,ss}$  and  $C_{max,ss}$  may be reported.

The following PK parameters will be calculated for diagnostic purposes and listed, but will not be summarized.

[figure not shown]
$t_{1/2}$ , Interval	The time interval (h) of the log-linear regression to determine $K_{el}$ .
$t_{1/2}$ , N	Number of data points included in the least squares log-linear regression analysis to determine $K_{el}$ . A minimum of the last 3 quantifiable data points excluding $t_{max,ss}$ will be used for determination.
Rsq	Goodness-of-fit statistic for calculation of $K_{el}$ (Regression coefficient).

Pharmacokinetic parameters will be summarized by treatment using descriptive statistics. Geometric mean will not be calculated for  $t_{max}$ . A subject listing of individual PK parameters for each treatment will be provided. For  $t_{max}$  a frequency table will also be provided.

Scatter plots of individual and mean PK parameters versus treatment will be presented. Additionally, graphical presentations of PK data may be added at the discretion of the PK scientists, if further illustration of the PK results is deemed appropriate.

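### SAP 18.3 writes Vd/Fss without brackets, so read literally it multiplies by AUC0-tau instead of dividing by it (minor; one-line correction)

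*SAP*

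**What the plan says.** The SAP and the protocol each define clearance and volume.

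- **SAP 18.3, clearance:** "Apparent oral systemic clearance, calculated as $Dose/AUC_{0-tau".
- **SAP 18.3, volume:** "Apparent oral volume of distribution, calculated as $Dose/K_{el} \times AUC_{0-tau". Nothing follows the subscript, and no brackets group Kel with AUC0-tau.
- **Protocol 6.13.2, clearance:** "Apparent oral clearance (calculated as Dose/AUC", where the AUC is the one extrapolated to infinity.
- **Protocol 6.13.2, volume:** "Apparent oral volume of distribution (calculated as oral clearance/ $K_{el".

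SAP 3.6 lists the departures from the protocol. For PK it declares only that the non-compartmental analysis moves to multiple dosing. SAP 6.5.2 names Phoenix WinNonlin as the software for these calculations. Under SAP 18.3 the PK parameters are summarised by treatment, listed by subject and plotted against treatment.

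**The concern.** Without brackets, a slash followed by a multiplication sign is evaluated from left to right, so the SAP entry becomes (Dose/Kel) × AUC0-tau. That conflicts with the clearance entry in the same table and with the protocol. The declared move to multiple dosing explains why AUC0-tau replaces AUCinf. It does not explain why AUC should move to the numerator.

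Characterising PK is a secondary objective, and the SAP presents itself as the source of rules for the PK analysis, so a programmer or checker may reasonably follow the line as it stands. The resulting error would grow with dose. In a plot of the parameter against treatment it would look like a dose-dependent volume, for a drug that the protocol describes as having dose-proportional exposure.

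**Working it through.** The documents give no numerical Vd/F, so there is no figure to reproduce. The check is algebra, units and a worked example.

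**1. What the formula should be.** Start from CL/Fss = Dose/AUC0-tau (SAP 18.3) and Vd/F = (CL/F)/Kel (Protocol 6.13.2):

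Vd/Fss = (Dose/AUC0-tau)/Kel = Dose/(Kel × AUC0-tau).

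**2. Units,** with dose in mg, Kel in 1/h and AUC in mg·h/L:

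- Bracketed: mg ÷ (1/h × mg·h/L) = L, a volume.
- Literal: mg ÷ (1/h) × mg·h/L = mg²·h²/L, not a volume.

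**3. Ratio of the two.** [(Dose/Kel) × AUC] ÷ [Dose/(Kel × AUC)] = AUC².

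**4. Behaviour across the doses of 75, 150 and 300 mg.** If AUC is proportional to dose, the literal expression is proportional to dose × dose. The ratios to the 75 mg value are (150/75)² = 4 and (300/75)² = 16, that is 1:4:16. The bracketed expression gives 1:1:1.

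**5. Worked example.** One-compartment oral model at steady state with a 24 h interval. The half-life of 5 h is the lower end of the range in Protocol 1.3.1, so Kel = ln(2)/5 = 0.1386 per h. V/F = 200 L is an assumption, because the documents give no value. AUC0-tau = Dose/(Kel × V/F).

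| Dose (mg) | AUC0-tau (mg·h/L) | Literal (mg²·h²/L) | Bracketed (L) |
|---|---|---|---|
| 75 | 2.705 | 1,463 | 200 |
| 150 | 5.410 | 5,854 | 200 |
| 300 | 10.820 | 23,415 | 200 |

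With V/F of 50 or 400 L and a half-life of 5 or 7.6 h the absolute values change. The 1:4:16 pattern does not, and the bracketed form returns the assumed V/F each time.

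**6. Sensitivity to dose proportionality.** Protocol 1.3.1 says of single and repeated twice-daily dosing that "JZP-110 exposure was dose-proportional", but it states linearity for a specific range: "JZP-110 displayed linear PK during 14 days of dosing over the dose range of 200 to 1000 mg per day". The 75 and 150 mg doses lie below 200 mg. This holds as free base, and also as salt: by the conversion in Protocol 1.3 (300 mg base is 356 mg salt) they are 356/300 × 75 = 89 mg and 356/300 × 150 = 178 mg. Suppose instead that AUC is proportional to Dose^b. The 300-to-75 mg ratio is then 4^(1+b) for the literal form and 4^(1−b) for the correct form.

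| b | Literal | Correct |
|---|---|---|
| 0.8 | 12.1 | 1.32 |
| 1.0 | 16.0 | 1.00 |
| 1.2 | 21.1 | 0.76 |

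**The case against.** The strongest reply is that this is a typographical slip with only one sensible reading. The entry contains exactly the terms of Dose/(Kel × AUC0-tau), in the right order, next to a clearance definition that settles the meaning. A fraction flattened in document conversion cannot be fully excluded, although stacked fractions in SAP 10.1 and 15.1 come through intact. This explanation of the cause stands, and it points to the same correction. It does not make the printed line right.

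Three stronger readings are tempting, and the documents do not support them.

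- *The reported volume will be wrong.* Nothing says that Vd/Fss will be hand-coded from the SAP text. SAP 6.5.2 gives the calculation to Phoenix WinNonlin, and a result in mg²·h²/L would be hard to pass off as litres. The exposure is to literal programming or literal quality checking.
- *The error is a fixed multiple of the true value.* AUC² carries units, so the multiple depends on the units chosen. In the example at 300 mg it is 10.82² = 117 with AUC in mg·h/L, and 10,820² = 1.17 × 10⁸ with AUC in ng·h/mL. Only the ratio between doses is free of units.
- *The trial's conclusions are at risk.* Protocol 9.11 names Cmax, Tmax, half-life and AUC as the parameters of interest, and Vd/F is not among them. PK sampling covers only subjects enrolled before Amendment 2, and the summaries are descriptive. AUC0-tau is itself extrapolated from 8 h of sampling to a 24 h interval, and the SAP warns about this, so Vd/Fss is already a weak parameter.

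**Conclusion.** The printed formula is wrong as written and conflicts with two other definitions in the documents; the conflict is not a declared change. Severity is minor. The 16-fold rise from 75 to 300 mg rests on two conditions: that the line is followed literally, and that AUC is proportional to dose over a range that extends below the 200 mg at which stated linearity begins. Modest departures from proportionality (b from 0.8 to 1.2) give a rise of about 12- to 21-fold, so the qualitative point survives. Safety, ESS and sample size are unaffected.

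**What to change.** In SAP 18.3, replace the Vd/Fss entry with Dose/(Kel × AUC0-tau), or equivalently (CL/Fss)/Kel. The second form leaves no room for a bracketing error. It matches Protocol 6.13.2 in form only, because the protocol's clearance uses AUCinf and the SAP's uses AUC0-tau. That difference is covered by the multiple-dose change in SAP 3.6 and needs no further action.

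The cost is one line of SAP text, with no analytical downside. If PK outputs or check programs already exist, confirm that Vd/Fss equals (CL/Fss)/Kel for each subject and dose.

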## 18.4. PHARMACOKINETIC/PHARMACODYNAMIC MODELING

Population pharmacokinetic and pharmacodynamic modeling may be used to explore exposure-response relationships using the data generated in this study. Any modeling performed will be conducted in accordance with a separate modelling data analysis plan and will be reported outside of the clinical study report.

## 19. DATA NOT SUMMARIZED OR PRESENTED

The other variables and/or domains not summarized or presented are:

- Comments

These domains and/or variables will not be summarized or presented, but will be available in the clinical study database, SDTM and/or ADaM datasets.

## APPENDIX 1. PARTIAL DATE CONVENTIONS

### ALGORITHM FOR TREATMENT EMERGENCE OF ADVERSE EVENTS

START DATE	STOP DATE	ACTION
Known	Known	
 
• If AE start date or worsened in severity < study drug first dose date, then not TEAE
 
• If study drug first dose date ≤ AE start date or worsened in severity ≤ (study drug last dose date + 30 days), then TEAE
 

	Partial	
 
• If AE start date or worsened in severity < study drug first dose date, then not TEAE
 
• If study drug first dose date ≤ AE start date or worsened in severity ≤ (study drug last dose date + 30 days), then TEAE
 

	Missing	
 
• If AE start date or worsened in severity < study drug first dose date, then not TEAE
 
• If study drug first dose date ≤ AE start date or worsened in severity ≤ (study drug last dose date + 30 days), then TEAE
 

Partial, but known components show that it cannot be on or after study drug first dose date	Known	Not TEAE
	Partial	Not TEAE
	Missing	Not TEAE
Partial, could be on or after study first dose date	Known	
 
• If AE stop date < study drug first dose date, then not TEAE
 
• If study drug first dose date ≤ AE worsened in severity or stop date ≤ (study drug last dose date + 30 days), then TEAE
 

	Partial	Impute AE stop date as latest possible date (i.e. last day of month if day unknown or 31st December if day and month are unknown), then: 
 
• If AE stop date < study drug first dose date, then not TEAE
 
• If study drug first dose date ≤ AE stop date ≤ (study drug last dose date + 30 days), then TEAE
 

	Missing	Assumed TEAE
Missing	Known	
 
• If AE stop date < study drug first dose date, then not TEAE
 
• If study drug first dose date ≤ AE stop date ≤ (study drug last dose date + 30 days), then TEAE
 

[figure not shown]
START DATE	STOP DATE	ACTION
	Partial	Impute AE stop date as latest possible date (i.e. last day of month if day unknown or 31st December if day and month are unknown), then: 
 
• If AE stop date < study drug first dose date, then not TEAE
 
• If study drug first dose date ≤ AE stop date ≤ (study drug last dose date + 30 days), then TEAE
 

	Missing	Assumed TEAE

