#### 6.14.1.6 Follow-up of Adverse Events and Serious Adverse Events

AEs and SAEs assessed as not related to study drug or procedure, including clinically significant laboratory tests, ECGs, or physical examination findings, must be followed until the event resolves, the condition stabilizes, the event is otherwise explained, or the final study visit occurs, whichever comes first.

AEs and SAEs assessed as related to study drug or procedure will be followed for as long as necessary to adequately evaluate the subject's safety, or until the event resolves, the condition stabilizes, the event is otherwise explained, or the subject is lost to follow up.

If the event resolves, a resolution date should be provided. For SAEs, a follow-up SAE Reporting form must be submitted to provide the final outcome of the event and if the event resolves, the resolution date.

The investigator is responsible for ensuring that follow-up includes any supplemental investigations indicated to elucidate the nature and/or causality of the AE. This may include additional clinical laboratory testing or investigations, examinations, histopathological examinations, or consultation with other health care professionals as is practical.

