## **9.13 Safety Analysis**

### **9.13.1 Adverse Events**

Adverse events will be coded using the Medical Dictionary for Regulatory Activities system to classify events under primary system organ class and preferred term. The number and percent of subjects who experienced TEAEs, TEAEs related to study drug, or SAEs; who died during the study; or who discontinued study drug or withdrew from the study due to an AE will be summarized by treatment at onset. Results will be presented by system organ class, and preferred term.

A TEAE is defined as an AE that either began after first study drug dose or worsened after the first dose. When determining the percent of subjects who experience an AE, multiple increases in severity are only counted as one AE. For example, a subject who develops a mild headache after the first study drug dose (that was not present during screening or at baseline), which subsequently worsens to moderate, then severe, is only counted once under the preferred term of headache.

For all AE summaries, if a subject has more than one AE within a preferred term on a given dose, the subject is counted only once at the maximum severity and with the closest relationship to study drug. If a subject has more than one AE within a system organ class, the subject is similarly counted once when reporting results for that system organ class.

All AE data will be listed.

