## 17.1. ADVERSE EVENTS

Adverse events will be coded to SOC and PT using the MedDRA dictionary (version 18.0) and will be classified as follows:

- **Prior AEs** are defined as AEs that started on or after the signature of the informed consent but prior to the first dose of study drug (i.e., first dose in Period 1) and have not worsened in severity on or after the first dose of study drug;
- **Treatment-emergent adverse events (TEAEs)** are defined as any AEs that started or worsened in severity on or after the first dose of study drug;

Only TEAEs will be summarized; listings will include all AEs (see APPENDIX 1 for handling of partial dates for AEs). AEs will be reported under the treatment group being received when AE first occurs/worsens. Should an AE with a partially missing onset date can be assigned to more than one treatment group, it will be reported under the active treatment group with the lowest dose. For TEAEs that started during the safety follow-up period, TEAEs will be attributed to the last treatment group received in the study.

An overall summary of number and percentage of subjects within each of the categories described in the following subsections (e.g., all TEAEs, SAEs, AEs leading to discontinuation of study drug, etc.) will be provided. A similar overall summary will be presented for the subset of TEAEs that started during the safety follow-up period.

For TEAEs summarized by SOC and PT, SOC will be sorted in alphabetical order and the PTs within each SOC will be sorted in descending frequency order for the pooled JZP-110 treatment group. For PT only tables, incidence will be sorted similarly to the PTs in the summaries by SOC and PT.

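### SAP Appendix 1 conflicts with the SAP's own definition of a treatment-emergent AE: it passes over worsening after a pre-dose start and leaves some AEs with incomplete onset dates without a class

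*SAP*

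**What the plan says.** SAP Section 17.1 defines TEAEs as "any AEs that started or worsened in severity on or after the first dose of study drug". An AE is Prior only if it began before first dose and did not worsen afterwards. Protocol Section 9.13.1 agrees: "A TEAE is defined as an AE that either began after first study drug dose or worsened after the first dose". Neither sets a condition on the stop date or an upper time limit. SAP Section 3.6, which lists the changes from the protocol, reports no change to this definition. Section 17.1 tabulates TEAEs only, lists all AEs, and sends the reader to Appendix 1 for partial dates.

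Appendix 1 crosses four kinds of start date with three kinds of stop date (known, partial, missing), which gives twelve cells.

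- **Start known (3 cells).** Not a TEAE if start or worsening precedes first dose. A TEAE if it falls between first dose and a limit of 30 days after last dose: "AE start date or worsened in severity ≤ (study drug last dose date + 30 days), then TEAE".
- **Start partial and certainly pre-dose (3 cells).** "Partial, but known components show that it cannot be on or after study drug first dose date": not a TEAE, whatever the stop date.
- **Start partial and possibly on or after first dose (3 cells).** With a known stop, the limit applies to worsening or stop: "If study drug first dose date ≤ AE worsened in severity or stop date". With a partial stop, it applies to the stop date alone.
- **Start missing (3 cells).** With a known or partial stop, "If study drug first dose date ≤ AE stop date ≤ (study drug last dose date + 30 days), then TEAE".

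In the last two groups a missing stop date means the AE is assumed to be a TEAE. A partial stop date is imputed to the latest possible day. No cell says what happens when the stop falls after the limit.

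**The concern.** Safety and tolerability are the primary objective, and treatment-emergent AEs head the list of measures in Protocol Section 9.8. The algorithm that decides which AEs enter the tables should give the same answer as the definition. It fails to do so in two places.

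An AE that was present before dosing and worsens afterwards is treatment-emergent by definition, but Appendix 1 either denies this or gives two answers. Separately, a late stop date says nothing about whether an AE emerged on treatment, yet in four cells it decides whether any rule applies.

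Late stop dates are foreseeable. Protocol Section 6.14.1.6 says "AEs and SAEs assessed as related to study drug or procedure will be followed for as long as necessary", whereas unrelated AEs are followed no further than the final visit, about 7 days after last dose. Known stop dates beyond the 30-day limit should therefore belong mainly to events judged related. If unclassified events are left out of the tables, TEAEs are under-counted.

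**Working it through.** The plan states no figure to reproduce. The check applies each cell literally and compares the result with Section 17.1. Take the nominal schedule: first dose Day 1, last dose Day 28, limit Day 28 + 30 = Day 58.

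**1. Pre-dose start, worsens Day 15, stops Day 25.** Section 17.1: TEAE, because 15 ≥ 1.

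- Start partial and certainly pre-dose: not a TEAE in all 3 cells. This contradicts the definition.
- Start known: both rules fire in all 3 cells. The start is before Day 1, so not a TEAE; worsening lies between Day 1 and Day 58, so TEAE. Appendix 1 states no order of precedence.
- Start partial and possibly on treatment, or missing: TEAE in all 6 cells.

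**2. Onset Day 20, no worsening, stops Day 70 (last dose + 42).** Section 17.1: TEAE, because 20 ≥ 1.

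| Start date | Stop known | Stop partial | Stop missing |
|---|---|---|---|
| Known | TEAE | TEAE | TEAE |
| Partial, possibly on treatment | no rule | no rule | TEAE |
| Missing | no rule | no rule | TEAE |

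Move the stop to Day 50 and all nine cells return TEAE. The stop date alone opens the gap.

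**3. Pre-dose start, worsens Day 15, stops Day 70.** The cell for a possibly on-treatment start with a known stop returns TEAE, because it accepts the worsening date. Three cells still have no rule: possibly on-treatment start with partial stop, and missing start with known or partial stop.

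**4. A calendar example.** First dose 1 March, last dose 28 March, limit 28 March + 30 days = 27 April. Onset recorded as March: every day of March is on or after first dose, so the AE is certainly treatment-emergent. Stop recorded as April: imputed to 30 April, which is later than 27 April. No rule fires. With no stop date at all, the same AE would be a TEAE.

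**5. How often imputation crosses the limit.** Taking each of the 365 days of 2018 as the last-dose date (the year is an assumption):

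- stop month is the last-dose month: 0/365, since a month end is at most 30 days away;
- stop month is the next month: 358/365 = 98%;
- only the stop year is known, and it is the last-dose year: 334/365 = 92% (last doses from 1 December escape).

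These are conditional figures. Now suppose instead that every stop date lacks its day, that true stops are spread evenly, that treatment lasts 28 days, and that last-dose dates cover 730 days. The share imputed past the limit is then 0% for stops during treatment, 2.3% for stops from first dose to last dose + 7 days, and 25% for stops from first dose to last dose + 30 days.

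**The case against.** The best defence is that Section 17.1 governs. It defines a TEAE fully and cites Appendix 1 only for partial dates. It also resolves the double answer in the known-start rows, since a Prior AE must not have worsened. A programmer who finds no rule could fall back on it. All of this is fair, but it does not rescue the cells where Appendix 1 states outright that the AE is not a TEAE. It also leaves the four open cells to be settled case by case.

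A second defence is recording practice. If a worsening is entered as a new AE with its own start date, the first problem shrinks. Protocol Section 6.14.1 does count worsening of a condition present at study start as an AE. The documents do not say how a worsened AE is entered.

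SAP Section 7.2 also mentions a post-treatment class of AEs, which might seem to take the late-stopping ones. It refers to Section 17.1.1 for that class, and no definition stands there or in the Section 17.1 introduction.

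Finally, the safety analysis is descriptive and AEs are reviewed at weekly visits, so incomplete onset dates should be uncommon. This bears on size and stands.

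**Conclusion.** Wrong as written, minor severity. Appendix 1 contradicts Section 17.1 in three cells, gives two answers in three more when a pre-dose AE worsens, and gives none in four when the stop is later than last dose + 30 days. In one of those four (possibly on-treatment start, known stop), a worsening date within the limit closes the gap. The effect is possible under-counting of TEAEs. The documents do not give the number of AEs with incomplete onset dates, so the count affected cannot be estimated; it is probably small.

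A reader might infer more than the documents support:

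- *Long-lasting related AEs drop out of the tables.* With a complete on-treatment onset date they remain TEAEs however long they last.
- *Late-stopping AEs are declared not treatment-emergent.* They are left unclassified. Omission from the tables is a likely programming result rather than stated text, and they stay in the listings.
- *Worsening is ignored for every partial onset.* One cell tests it explicitly.
- *Imputation moves most partial stop dates past the limit.* The 98% and 92% hold only for particular stop months or years; a stop in the last-dose month never crosses it.
- *The loss always flatters the drug.* The rule takes no account of treatment, and AEs in placebo periods, including Sequence C, fall into the same gap.

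**What to change.** Align Appendix 1 with Section 17.1 before unblinding:

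1. Test the start or worsening date in every row.
2. Let worsening on or after first dose override a not-TEAE result, both in the rows with a certainly pre-dose partial start and in the known-start rows.
3. Use the stop date only to show that an AE ended before first dose.
4. Otherwise, where onset is partial or missing and could be on or after first dose, assume TEAE.
5. If a limit of last dose + 30 days is kept, apply it only to the start or worsening date and state it in Section 17.1, which now has none.

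The cost is a change of wording in Appendix 1 (and one sentence in Section 17.1 if the limit stays) and one derivation program. No extra data are needed. TEAE counts could rise slightly.
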